# **RIGID-TyG: assessment of arterial stiffness and its association with metabolic indices based on triglycerides and glucose**

## **1. ABSTRACT**

Systemic arterial hypertension remains one of the main causes of cardiovascular morbidity and mortality worldwide, and its evaluation should not be restricted to mean blood pressure (BP) levels. Vascular and metabolic markers have expanded the understanding of cardiovascular risk, particularly carotid–femoral pulse wave velocity (cfPWV), considered the gold standard for the assessment of arterial stiffness, and the triglyceride–glucose (TyG) index, recognized as an indirect marker of insulin resistance.

Evidence suggests that insulin resistance, central adiposity, and vascular dysfunction share common pathophysiological mechanisms, including endothelial dysfunction, low-grade inflammation, sympathetic activation, and arterial remodeling. These mechanisms may contribute both to increased arterial stiffness and to alterations in circadian blood pressure regulation, particularly in the morning period, when a physiological rise in blood pressure levels occurs. When exaggerated, this phenomenon, known as morning blood pressure surge (MBPS), is associated with increased cardiovascular risk.

The present study aims to evaluate the association between carotid–femoral pulse wave velocity (cfPWV) and metabolic indices, including the TyG index and its derived metrics (TyG-WC, TyG-BMI, and TyG-WHtR), as well as composite indices such as the body roundness index (BRI), the metabolic score for insulin resistance (METS-IR), and the cardiometabolic index (CMI). Additionally, morning blood pressure and MBPS will be investigated across different metabolic profiles.

This is an observational, cross-sectional study with prospective collection of clinical, anthropometric, laboratory, and hemodynamic data in individuals referred for ambulatory blood pressure monitoring (ABPM). The results are expected to contribute to the integration of accessible metabolic markers with arterial stiffness parameters and morning hemodynamic load, improving cardiovascular risk stratification in individuals with suspected hypertension or untreated hypertension.

## **2. OBJECTIVES**

### **2.1 Primary objective**

To evaluate the association between arterial stiffness measured by carotid–femoral pulse wave velocity (cfPWV) and the triglyceride–glucose index.

### **2.2 Secondary objectives**

To evaluate the association between derived metrics of the triglyceride–glucose index, including TyG-WC, TyG-BMI, and TyG-WHtR, and cfPWV values.

To evaluate the association between composite metabolic indices, including METS-IR and CMI, and cfPWV.

To evaluate the relationship between metabolic indices (TyG, TyG-WC, TyG-BMI, TyG-WHtR, METS-IR, and CMI) and morning blood pressure and MBPS.

To compare the performance of different metabolic and anthropometric indices in identifying individuals with increased arterial stiffness and higher morning hemodynamic load.

### **3. THEORETICAL BACKGROUND**

Systemic arterial hypertension remains one of the main determinants of cardiovascular morbidity and mortality at a global level, showing a continuous and progressive relationship with adverse events, including myocardial infarction, stroke, and heart failure [1]. Evidence from large population-based studies demonstrates that even modest increases in blood pressure (BP) are associated with a significant increase in cardiovascular risk, reinforcing the need for more comprehensive risk stratification strategies beyond conventional office BP measurements [2–3].

In this context, the incorporation of vascular markers has enabled a better understanding of cardiovascular pathophysiology. Arterial stiffness (AS), particularly assessed by carotid–femoral pulse wave velocity (cfPWV), is considered the gold standard for the non-invasive evaluation of aortic stiffness and shows a strong independent association with cardiovascular events and mortality [4]. Increased cfPWV reflects structural and functional alterations of the arterial wall, including elastin fragmentation, increased collagen content, vascular calcification, and endothelial dysfunction, representing an integrated marker of cumulative vascular damage [5–6].

In parallel, insulin resistance plays a central role in the pathophysiology of cardiometabolic diseases. This metabolic state is associated with reduced nitric oxide bioavailability, increased sympathetic nervous system activity, chronic low-grade inflammation, and vascular remodeling, mechanisms directly involved in the development of arterial stiffness [7–8]. The triglyceride–glucose (TyG) index, derived from widely available laboratory parameters, has been validated as a reliable surrogate marker of insulin resistance, showing consistent associations with type 2 diabetes mellitus, subclinical atherosclerosis, and cardiovascular events [9–10].

In addition to the TyG index alone, derived metrics that incorporate anthropometric parameters, such as the triglyceride–glucose index combined with waist circumference (TyG-WC), the triglyceride–glucose index combined with body mass index (TyG-BMI), and the triglyceride–glucose index combined with the waist-to-height ratio (TyG-WHtR), have been proposed with the aim of more comprehensively capturing the interaction between metabolism and adiposity, particularly central adiposity, which is recognized as an important determinant of cardiovascular risk [11–13]. However, other composite indices have been developed to integrate multiple pathophysiological domains.

In this context, the body roundness index (BRI), derived from waist circumference and height, provides a geometric estimate of body fat distribution and has been associated with visceral adiposity and cardiometabolic alterations [14]. Complementarily, the metabolic score for insulin resistance (METS-IR), which integrates fasting glucose, triglycerides, body mass index, and HDL-cholesterol, allows for a more comprehensive assessment of insulin resistance [15], while the cardiometabolic index (CMI), based on the waist-to-height ratio and lipid profile, reflects the interaction between central adiposity and dyslipidemia [16].

These indices may provide incremental value over isolated markers by integrating multiple pathophysiological pathways involved in vascular dysfunction. Central adiposity, insulin resistance, and lipid abnormalities are associated with endothelial dysfunction, increased sympathetic activity, chronic low-grade inflammation, and vascular remodeling, mechanisms directly related to increased arterial stiffness [5]. In this context, higher values of BRI, METS-IR, and CMI may be associated with increased cfPWV, reflecting greater impairment of arterial compliance.

Another relevant dimension of cardiovascular pathophysiology is the circadian variability of blood pressure. The awakening period is characterized by a physiological increase in BP, mediated by sympathetic activation, increased catecholamine release, and hormonal changes, including cortisol. When exaggerated, this phenomenon, known as morning blood pressure surge (MBPS), has been associated with a higher incidence of cardiovascular events, particularly stroke and coronary events [17–21].

From a hemodynamic perspective, arterial stiffness (AS) may amplify this morning BP increase, since less compliant arteries have a reduced capacity to buffer the pulse wave, resulting in greater transmission of pulsatile pressure to the peripheral and microvascular circulation. In addition, metabolic dysfunction may interfere with autonomic regulation and baroreflex sensitivity, contributing to alterations in the circadian control of BP [22–23].

Despite the biological plausibility and clinical relevance of these interactions, the integrated relationship between metabolic indices derived from insulin resistance, anthropometric markers of central adiposity, arterial stiffness, and morning BP parameters remains insufficiently explored. Understanding these mechanisms may provide new insights

into the pathophysiology of hypertension in its early stages and contribute to the identification of phenotypes at higher cardiovascular risk, even in apparently normotensive individuals.

Therefore, the present study aims to evaluate the association between arterial stiffness, measured by cfPWV, and metabolic and anthropometric indices, including TyG and its derived metrics, BRI, METS-IR, and CMI, as well as to investigate their relationship with morning BP and MBPS, integrating metabolic, structural, and functional dimensions of cardiovascular pathophysiology.

#### **4. JUSTIFICATION**

The assessment of cardiovascular risk needs to go beyond traditional blood pressure (BP) measurements, incorporating markers that reflect early structural and metabolic changes. Arterial damage, assessed by cfPWV, is a well-established marker of subclinical vascular damage, while the TyG index and its derived analyzes represent simple and accessible alternatives for estimating insulin resistance and metabolic dysfunction. Despite the wide availability of metabolic indices, their relationship with direct markers of arterial stress is still not fully established, especially when multiple derived and composite indices are included within the same analytical model. In addition, the interaction between these markers and the hemodynamic load during the morning period, a critical phase of the circadian cycle associated with a higher incidence of cardiovascular events, remains poorly explored.

Prospective data collection allows greater control over measurement quality, standardization of protocols, and reduction of biases inherent to secondary analyses. This design makes it possible to integrate, in a simultaneous and systematic manner, clinical, laboratory, and hemodynamic variables, bringing the results closer to real-world clinical practice conditions. Therefore, the present study is justified by the need to investigate, in an integrated manner, the relationship between metabolic dysfunction, arterial impairment, and morning blood pressure behavior, contributing to the development of more precise cardiovascular risk stratification strategies.

#### **5. METHODS**

##### **5.1 Study design and data sources**

This is an observational, cross-sectional study with a prospective component. The study will use data derived from two complementary sources: (1) data previously collected in a research project approved by the Research Ethics Committee of the Faculdade de Medicina de São José do Rio Preto – FAMERP – SP in 2022 (CAEE 57703722.7.0000.5415) and (2) data obtained prospectively according to the standardized protocol established in the present study. The previously collected data refers to participants evaluated within the context of the prior protocol approved by the Research Ethics Committee and will be used secondarily, with assurance of confidentiality and anonymization of the information.

Additionally, new participants will be prospectively included, with collection of clinical, anthropometric, laboratory, and hemodynamic data performed according to the protocol described in this study, after signing the informed consent form. The study population will consist of adults referred for ambulatory blood pressure monitoring (ABPM) in a specialized center for the diagnosis and follow-up of cardiovascular diseases.

Data collection will be performed within the clinical care setting, concurrently with routine clinical evaluation, including office blood pressure measurements, anthropometric measurements, 24-hour ABPM, cfPWV measurement, and the acquisition of laboratory parameters required for the calculation of metabolic indices. To ensure comparability between previously collected data and prospectively obtained data, equivalent methodological criteria will be adopted, including standardized protocols for blood pressure measurement, assessment of arterial stiffness by cfPWV, and uniform definition of clinical and laboratory variables.

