### **5.14 Statistical analysis**

Continuous variables will be described as mean and standard deviation or median and interquartile range, according to data distribution, while categorical variables will be presented as absolute frequencies and proportions. Normality will be assessed using appropriate methods prior to the selection of comparative tests.

For the analysis of secondary objectives, participants will be distributed into TyG quartiles. Comparisons between quartiles will be performed using analysis of variance (ANOVA) or the corresponding test, with calculation of *p* for trend when appropriate. Analyses may be repeated after stratification by hypertension status, in order to evaluate differential behavior of morning parameters between normotensive and untreated hypertensive individuals.

The association between cfPWV and TyG, as well as between TyG and morning BP parameters, will be evaluated using univariable and multivariable linear regression models. Covariates will be selected a priori based on biological plausibility and prior evidence, including age, sex, BMI, mean 24-hour systolic and diastolic BP, hypertension status, and other clinically relevant variables. Interaction terms will also be explored, particularly between TyG metrics and hypertension status.

Considering the analytical tradition of the group in arterial stiffness studies, additional methods of agreement and bias assessment may be employed to explore relationships between continuous variables when appropriate, including Lin's concordance correlation coefficient and Bland–Altman analysis. The level of statistical significance will be set at 5% in two-tailed tests.

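### Data from a prior protocol and new data feed one TyG–cfPWV regression; naming data source as a covariate and reporting by source would guard against a source offset at almost no cost

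*Protocol*

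**What the plan says.** Section 5.1 states: "The study will use data derived from two complementary sources". On the first source it says: "The previously collected data refers to participants evaluated within the context of the prior protocol approved by the Research Ethics Committee". The second source is "data obtained prospectively according to the standardized protocol established in the present study". Comparability rests on one sentence, which opens "To ensure comparability between previously collected data and prospectively obtained data, equivalent methodological criteria will be adopted" and goes on to mention standardized blood pressure and cfPWV protocols and uniform variable definitions. The earlier project's devices and procedures are not described.

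Section 5.14 says that the association of cfPWV with TyG "will be evaluated using univariable and multivariable linear regression models". On adjustment it says: "Covariates will be selected a priori based on biological plausibility and prior evidence". It then names age, sex, BMI, mean 24-hour systolic and diastolic pressure and hypertension status, and leaves room for further variables of clinical relevance. Section 5.12 gives a similar list with waist circumference added. The only stratification and the only specific interaction named are by hypertension status. Data source appears in neither section.

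The abstract opens its design statement with "This is an observational, cross-sectional study with prospective collection of clinical, anthropometric, laboratory, and hemodynamic data" and does not mention the secondary data. Section 4 argues: "Prospective data collection allows greater control over measurement quality, standardization of protocols, and reduction of biases inherent to secondary analyses".

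**The concern.** A promise about criteria to be adopted cannot reach back to completed measurements. Some things can still be harmonised on stored data: eligibility, index formulas, the morning blood pressure definitions and, if single readings were kept, the 0.5 m/s agreement rule of section 5.10. Others cannot: the cfPWV device, the rest period, the number of cfPWV readings taken, the waist site of section 5.6 and the conduct of the blood pressure measurements. For these, equivalence is asserted rather than shown.

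If one source has higher cfPWV for technical or case-mix reasons that the covariates do not capture, and also has higher or lower TyG, a regression without a source term reads part of that offset as a TyG effect. The primary objective is exactly this association. Without a by-source estimate, a reader also cannot see whether the new data alone support the result.

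**Working it through.** The protocol gives no sample size, SD, effect size or split between sources, so there is no figure of its own to reproduce. Every numerical input below is an assumption.

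**Formula.** Let p be the share from one source, δT the between-source difference in mean TyG, δP the between-source cfPWV offset at equal TyG, and σ the within-source SD of TyG. With source left out, the unadjusted slope absorbs δP × Cov(source, TyG) / Var(TyG), so

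bias = p(1−p)·δT·δP / [σ² + p(1−p)·δT²].

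It is exactly zero when δT = 0 or δP = 0, and negative when the two have opposite signs.

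**Values, σ = 0.6 (σ² = 0.36).**

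- Middle case, p = 0.5, δT = 0.2, δP = 0.5 m/s: 0.25 × 0.2 × 0.5 / (0.36 + 0.25 × 0.04) = 0.025 / 0.37 = 0.068 m/s per TyG unit.
- Low end, p = 0.3, δT = 0.1, δP = 0.3: 0.21 × 0.1 × 0.3 / (0.36 + 0.21 × 0.01) = 0.0063 / 0.3621 = 0.017.
- High end, p = 0.5, δT = 0.3, δP = 1.0: 0.25 × 0.3 × 1.0 / (0.36 + 0.25 × 0.09) = 0.075 / 0.3825 = 0.196.
- Middle case with opposite signs: −0.068.

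**Scale.** With an assumed cfPWV SD of 1.8 m/s and a correlation of 0.15–0.20, the slope is r × 1.8 / 0.6 = 0.45–0.60 m/s per TyG unit. The middle case is 0.068 / 0.60 = 11% to 0.068 / 0.45 = 15% of it.

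**Raw difference versus offset.** δP must be the difference at equal TyG. If 0.5 m/s were the raw difference and the true slope were 0.5, the offset would be 0.5 − 0.2 × 0.5 = 0.4, and the bias 0.25 × 0.2 × 0.4 / 0.37 = 0.054.

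**Simulation.** Assumptions: n = 400, p = 0.5, residual SD 1.5 m/s, 2,000 runs per scenario, 5% two-sided test, no other covariates. The TyG shift is in within-source SDs and the bias is from the formula, per SD. The last two columns give rejection when the true slope is zero.

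| TyG shift | cfPWV offset (m/s) | Bias (m/s per SD) | No source term | Source term |
|---|---|---|---|---|
| 0 | 0.5 | 0 | 4.8% | 4.6% |
| 0.2 | 0.5 | 0.025 | 7.1% | 5.6% |
| 0.5 | 0.5 | 0.059 | 12.9% | 5.7% |
| 0.5 | 1.0 | 0.118 | 32.1% | 5.6% |

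With a true slope of 0.20 per SD, the model with a source term returned 0.199–0.200 in every scenario. With no TyG shift, power was 74.2% without the term and 75.7% with it.

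**The case against.** The strongest reply is that a source indicator and by-source estimates are ordinary content of an analysis plan that is not shown, that section 5.14 leaves its covariate list open, and that the protocol never says the data will be pooled without a source term. This stands in part: pooling without the term is inferred from a single population and a single set of models. But section 5.1 itself raises comparability and offers a remedy that cannot fully work, and section 5.14 already fixes the named covariates, strata and interaction. Naming source there closes a gap that the protocol opens.

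Several stronger readings are tempting and are not supported:

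- *That source differences do confound the slope.* Nothing shows that the sources differ in TyG or cfPWV. The earlier project may have used the same methods, and 5.1 can be read as matching the new collection to them.
- *That covariates are chosen on biology alone.* Section 5.14 also invokes prior evidence.
- *That the study claims freedom from secondary-analysis bias.* Section 4 claims a reduction, and only for prospective collection. Sections 5.1 and 5.15 disclose the secondary use.
- *That laboratory variation is peculiar to the earlier data.* Section 5.11 takes routine reports for both.
- *That the earlier data were examined before the hypothesis was set, or that people appear twice.* Neither is documented. Section 5.4 simply has no exclusion for earlier participation.

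The size is also open to challenge. The formula is for the unadjusted model; age, sex, BMI and 24-hour pressure would absorb part of any case-mix difference, though not an offset from technique.

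**Conclusion.** The point holds as a possibility that the plan leaves unguarded. The comparability safeguard cannot change completed measurements, and the named models contain nothing that would remove or reveal a source offset. The pooled slope may then be biased upward or downward.

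The range of about 0.02–0.20 m/s per TyG unit applies to the unadjusted slope under assumed same-sign shifts; zero and negative values are equally compatible with the documents. The wording gap is smaller: the abstract and section 4 present the prospective side only, which is incomplete beside 5.1 rather than a false claim. This is best treated as a free improvement.

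**What to change.** - In section 5.14, name data source (prior project or present study) as a fixed covariate in the regression models.
- Report the primary TyG–cfPWV estimate in each source with a TyG-by-source interaction, and name the prospective-only estimate as a sensitivity analysis. This is needed because a source term removes only an additive offset, not a different slope or different measurement error.
- In section 5.1, describe how the earlier cfPWV, waist and blood pressure measurements were made, and which rules will be reapplied to stored data.
- Check for people present in both sources before anonymisation, since overlap may be untraceable afterwards.
- State in the abstract and section 4 that part of the data is secondary.

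The cost is one degree of freedom for an indicator that should be known for every participant, a few extra estimates and some wording. If the sources do differ in TyG, the term also gives up the between-source contrast. At unchanged residual variance this raises the variance of the unadjusted slope by 0.37 / 0.36 − 1 = 3% in the middle case and 0.3825 / 0.36 − 1 = 6% at the high end.

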## **5.2 Study setting and clinical context**

Participants will be evaluated in a specialized center for the diagnosis and follow-up of cardiovascular diseases, within the context of clinical diseases referral for ambulatory blood pressure monitoring. This setting includes individuals referred by the attending physician for diagnosis clarification of arterial hypertension, investigation of elevated office BP, or better characterization of the 24-hour blood pressure profile.

## **5.3 Study population**

Adults aged 18 to 65 years, of both sexes, will be included, who undergo ABPM as part of routine clinical evaluation and who are not using antihypertensive medication at the time of inclusion. The focus on untreated individuals aims to reduce the potential confounding effect of antihypertensive treatment on arterial stiffness, morning blood pressure, and indices derived from ABPM.

## **5.4 Inclusion and exclusion criteria**

Individuals who meet all of the following criteria will be included in the study:

- Age between 18 and 65 years;
- Both sexes;
- Referral for ambulatory blood pressure monitoring (ABPM) as part of clinical evaluation;
- Not using antihypertensive medication at the time of inclusion;
- Availability of complete office blood pressure data and valid ABPM recordings;
- Undergoing arterial stiffness assessment by carotid–femoral pulse wave velocity (cfPWV);
- Availability of laboratory tests including fasting glucose and triglycerides for calculation of the triglyceride–glucose (TyG) index;
- Agreement to participate in the study by signing the informed consent form (for prospective participants).

Individuals presenting any of the following conditions will be excluded from the study:  
Current use of antihypertensive medication;

- Cardiac arrhythmias that compromise the accuracy of blood pressure measurements or cfPWV;
  - ABPM recordings with inadequate quality or an insufficient number of valid measurements;
  - Clinical conditions that prevent or compromise adequate cfPWV measurement;
  - Severe vascular diseases or anatomical alterations that preclude pulse wave analysis;
  - Absence of essential data for calculation of metabolic indices or evaluation of the primary outcomes;
  - Refusal to participate in the study or absence of a signed informed consent form (for prospective data collection).

